2.7.1.8 Bath ankylosing spondylitis metrology index and chest expansion (BASMI)

The BASMI is a validated instrument that uses the minimum number of clinically appropriate measurements that assess accurately axial status, with the goal to define clinically significant changes in spinal movement. Parameters include:

1. Lateral spinal flexion (cm)
2. Tragus-to-wall distance (cm)
3. Lumbar flexion (modified Schober) (cm)
4. Maximal intermalleolar distance (cm)
5. Cervical rotation angle (°)

Additionally, the following assessments should be taken:

6. Chest expansion
7. Occiput-to-wall distance

The individual conversion of BASMI categories is as below.

1. Lateral lumbar flexion (cm)

Side	Standing	Bending	Difference	Larger difference	Mean of larger difference
Right	Reading 1	xx	xx	xx	xx*
	Reading 2	xx	xx	xx	
Left	Reading 1	xx	xx	xx	xx*
	Reading 2	xx	xx	xx	

Find the difference of standing and bending position for all readings, take largest difference from each side and use average of larger difference of both sides.

2. Tragus-to-wall distance* (cm)

	Right (1)	Left (2)	Average of (1) and (2)	Shortest average
Reading 1	xx	xx	xx	xx**
Reading 2	xx	xx	xx	

Find the average of both sides (right and left) for all readings and use shortest average.

3. Modified Schober Index (Lumbar flexion*) (cm)

	Bending	Difference (minus 15 cm standing distance)	Higher difference
Reading 1	xx	xx-15	xx**
Reading 2	xx	xx-15	

Subtract 15 from all readings and use higher difference.

4. Intermalleolar distance (cm)

Reading 1	Reading 2	Higher of Reading 1 and Reading 2
xx	xx	xx**

Use higher value from all readings.

5. Cervical rotation angle*(°)

Side	Reading 1	Reading 2	Higher of Reading 1 and Reading 2	Mean of higher reading
Right	xx	xx	xx*	xx**
Left	xx	xx	xx*	

Find the higher reading from both sides and use mean of higher reading.

6. Chest expension

	Inspiration	Expiration	Difference	Higher diffrence
Reading 1	xx	xx	xx*	xx**
Reading 2	xx	xx	xx*	

Find the higher reading from both sides and use higher difference.

After finalizing individual BASMI score (**) use below method to convert each BASMI score to a 0 to 10 scale.

The assessment A of the first five components is transformed into the scores S using the equations given in table below (van der Heijde et al 2006). The average score of the five assessments S gives the BASMI linear result. All 5 components must be available to calculate the score.

Table 2-3 Equations for the conversion of the assessments A into scores S for the 5 components of the BASMI linear

	S=0	Between 0 and 10	S=10
Lateral lumbar flexion* (cm)	$A \geq 21.1$	$S = (21.1 - A)/2.1$	$A \leq 0.1$
Tragus-to-wall distance* (cm)	$A \leq 8$	$S = (A - 8)/3$	$A \geq 38$
Lumbar flexion (modified Schober) (cm)	$A \geq 7.4$	$S = (7.4 - A)/0.7$	$A \leq 0.4$
Intermalleolar distance (cm)	$A \geq 124.5$	$S = (124.5 - A)/10$	$A \leq 24.5$
Cervical rotation angle*(°)	$A \geq 89.3$	$S = (89.3 - A)/8.5$	$A \leq 4.3$

* For lateral lumbar flexion, tragus-to-wall distance, and cervical rotation the average of right and left should be taken.

If a score lies beyond the range 0-10, the values 0 or 10 have to be used, respectively.

The BASMI linear is the mean of the five scores.

The BASMI linear will be summarized descriptively (total score change, from Baseline) by treatment group and overall, at Week 12, Week 24 [REDACTED] for FAS. The between-treatment difference in change from Baseline in BASMI linear will be evaluated using a MMRM. Treatment group and analysis visit as factors and Baseline BASMI score and weight as continuous covariates will be included in the model. Treatment group by analysis visit and Baseline BASMI score by analysis visit will be included as interaction terms in the model. An unstructured covariance matrix will be assumed. The treatment effect for the secukinumab T2T regimen at different analysis visits will be determined from the pairwise comparison performed between the 2 treatment groups.

The two additional assessments (chest expansion and occiput-to-wall distance) will be shown in the listing for BASMI for each treatment group.

2.7.1.9 Change in patient's/physician's global assessment of disease activity

[figure not shown]
The patient's/physician's global assessment score (VAS scale) will be collected in eCRF at scheduled visits. The patient's global assessment of disease activity will be performed using a 100 mm VAS ranging from not severe to very severe, after the question "How active was your disease on average during the last week?". The physician's global assessment of disease activity will be performed using 100 mm VAS ranging from no disease activity to maximal disease activity, after the question "Considering all the ways the disease affects your patient, draw a line on the scale for how well his or her condition is today.".

The patient's/physician's global assessment score will be summarized descriptively (total score change from Baseline) by treatment group and overall, at Week 12, Week 24 [REDACTED] for FAS.

The between-treatment difference in change from Baseline in patient's global disease assessment will be evaluated using a MMRM. Treatment group and analysis visit as factors and Baseline patient's global disease assessment VAS score and weight as continuous covariates will be included in the model. Treatment group by analysis visit and Baseline patient's global disease assessment VAS score by analysis visit will be included as interaction terms in the model. An unstructured covariance matrix will be assumed. The treatment effect for the

secukinumab T2T regimen at different analysis visits will be determined from the pairwise comparison performed between the 2 treatment groups.

Same methodology will be repeated for physician's global assessment of disease activity with associated changes for Baseline values.

[REDACTED]

[REDACTED]

[REDACTED]

[REDACTED]

2.7.1.12 ASAS health index

The ASAS-HI is a disease-specific questionnaire that was developed based on the comprehensive International Classification of Functioning, Disability and Health Core Set (also known as the ICF Core Set) for AS ([Kiltz et al 2014](#)). The ASAS HI is a linear composite measure and contains 17 items (dichotomous response option: “I agree” and “I do not agree”), which cover most of the international classification of functioning (ICF) Core Set. The ASAS HI contains items addressing categories of pain, emotional functions, sleep, sexual function, mobility, self-care, and community life. The total sum of the ASAS HI ranges from 0 to 17, with a lower score indicating a better health status.

A total score can be analyzed if no more than 20% of the data (i.e. 3 items) are missing. The total score is calculated as follows for respondents with one to a maximum of three missing responses: Total score = $(x / 17-m)*17$, where x=item summation score and m number of missing items. Cases with more than three missing responses cannot be allocated a total score.

In addition, the Environmental Factor (EF) Item Set contains items addressing categories of support/relationships, attitudes and health services. The EF Item Set contains 9 dichotomous items with an identical response option but without a sum score because of its multidimensional nature ([Kiltz et al 2014](#)).

The ASAS-HI will be summarized descriptively (total score, change from Baseline) by treatment group and overall at Week 12, Week 24 [REDACTED] for FAS. The between-treatment difference in change from Baseline in ASAS-HI will be evaluated using a MMRM. Treatment group and analysis visit as factors and Baseline ASAS-HI score and weight as continuous covariates will be included in the model. Treatment group by analysis visit and Baseline ASAS-HI score by analysis visit will be included as interaction terms in the model. An unstructured

covariance matrix will be assumed. The treatment effect for the secukinumab T2T regimen at different analysis visits will be determined from the pairwise comparison performed between the 2 treatment groups.

2.7.1.13 Short form-36 version 2 (acute form)

The following variables will be evaluated:

- SF-36 domain scores
- SF-36 PCS and MCS
- SF-36 responder analyses

The Short Form Health Survey (SF-36) is a widely used and extensively studied instrument to measure health-related quality of life among healthy subjects and patients with acute and chronic conditions. It consists of eight subscales (domains) that can be scored individually: Physical Functioning, Role-Physical, Bodily Pain, General Health, Vitality, Social Functioning, Role- Emotional, and Mental Health (Ware and Sherbourne 1992). Two overall summary scores, the Physical Component Summary (PCS) and the Mental Component Summary (MCS) also can be computed (Ware and Sherbourne 1992). The SF-36 has proven useful in monitoring general and specific populations, comparing the relative burden of different disease, differentiating the health benefits produced by different treatments, and in screening individual patients. The 8 domains are based on a scale from 0-100 while PCS and MCS are norm-based scores with a mean of 50 and a standard deviation of 10.

Quality metric uses weighted maximum likelihood estimation, a modified version of item response theory (IRT) to estimate scale scores when a respondent is missing multiple items. The PCS summary score measure requires scores for seven scales, one of which must be the PF scale and the MCS score also requires scores for seven scales, one of which must be the MH scale. Only one item is needed for each of the multi-item domains.

The SF-36 summary scores, PCS and MCS will be summarized descriptively (total score, change from Baseline) by treatment group and overall at Week 12, Week 24 [REDACTED] for FAS. For the change in SF-36 summary scores, PCS and MCS between-treatment differences will be evaluated utilizing a MMRM for full analysis set. Treatment group and analysis visit will be included as categorical factors in the model and Baseline SF-36 score (PCS or MCS) and weight as continuous covariates. Treatment group by analysis visit and Baseline SF-36 score (PCS or MCS respectively) by analysis visit will be included as interaction terms in the model. An unstructured covariance matrix will be assumed. The treatment effect for the secukinumab T2T regimen at different analysis visits will be determined from the pairwise comparison performed between the 2 treatment groups.

For the responder analyses the proportion of patients achieving a clinically meaningful difference in SF-36 summary score, PCS(=3.4) and MCS(=4.6) at Week 24 will be analyzed by means of a multiple logistic regression model with treatment and center as factors and weight and Baseline score value as continuous covariates.

2.7.1.14 Ankylosing spondylitis quality of life

The ASQoL is a self-administered questionnaire designed to assess health-related quality of life in adult patients with AS. The ASQoL contains 18 items with a dichotomous yes/no response

option. A single point is assigned for each “yes” response and no points for each “no” response resulting in overall scores that range from 0 (least severity) to 18 (highest severity). As such, lower scores indicate better quality of life. Items include an assessment of mobility/energy, self-care and mood/emotion. The recall period is “at the moment,” and the questionnaire requires approximately 6 minutes to complete. The purpose of the ASQoL is to assess the disease specific QoL of patients in this study.

At least 15 answered questions are required to be able to calculate ASQoL using mean imputation, (sum of answered)/(number answered)*18 ([Doward et al 2003](#)).

The ASQoL will be summarized descriptively (total score, change from Baseline) by treatment group and overall at Week 12, Week 24 [REDACTED] for FAS. Between-treatment differences in the change from Baseline in the ASQoL will be evaluated using a MMRM with treatment group and analysis visit as factors as well as Baseline ASQoL score and weight as continuous covariates. Treatment group by analysis visit and Baseline ASQoL by analysis visit will be included as interaction terms in the model. An unstructured covariance matrix will be assumed. The treatment effect for the secukinumab T2T regimen at different analysis visits will be determined from the pairwise comparison performed between the 2 treatment groups.

2.7.1.15 Functional assessment of chronic illness therapy – fatigue

The Functional Assessment of Chronic Illness Therapy - Fatigue (FACIT-Fatigue©) is a 13-item questionnaire ([Cella et al 1993](#), [Yellen et al 1997](#)) that assesses self-reported fatigue and its impact upon daily activities and function. The purpose of FACIT-Fatigue in this study is to assess the impact of fatigue on patients with AS.

Subjects respond to each item on a 5-point Likert-type scale (0 = not at all; 1 = a little bit; 2 = somewhat; 3 = quite a bit; 4 = very much) based on their experience of fatigue during the past 2 weeks. The scale score is computed by summing the item scores, after reversing those items that are worded in the negative direction (i.e. original response of 0 gets mapped to 4, 1=3, 2=2, 3=1, and 4=0). Numbering the questions from 1 to 13, it is evident that questions 7 and 8 are worded in the positive direction (4 indicates a desirable response) and all other questions are worded in the negative directions (4 indicates an undesirable response). Thus, it is necessary to reverse the responses for all questions except 7 and 8 for scoring purposes. When there are missing item scores, the scale score was computed by summing the non-missing item scores, multiplying by 13 (the total number of items in the scale) and dividing by the number of non-missing items (i.e. normalizing the results). The latter rule applied only when at least half of the items (seven or more) are non-missing. FACIT Fatigue scale score range from 0 to 52, where higher scores represent less fatigue ([Cella et al 1993](#)).

The FACIT-Fatigue will be summarized descriptively (total score change from Baseline) by treatment group and overall at Week 12, Week 24 [REDACTED] for FAS. Between-treatment differences in the change from Baseline in the FACIT-Fatigue total score will be evaluated using a MMRM with treatment group and analysis visit as factors as well as Baseline FACIT-Fatigue score and weight as continuous covariates. Treatment group by analysis visit and Baseline FACIT-Fatigue score by analysis visit will be included as interaction terms in the model. An unstructured covariance matrix will be assumed. The treatment effect for the secukinumab T2T regimen at different analysis visits will be determined from the pairwise comparison performed between the 2 treatment groups.

2.7.2 Statistical hypothesis, model, and method of analysis

Between-treatment comparisons for binary variables in the FAS population (e.g. ASAS20, ASAS40) at individual analysis visits will be evaluated using a logistic regression model with treatment and center as factors and weight as covariates. Odds ratios and 95% CI will be presented for appropriate treatment comparisons. Continuous variables will be evaluated, using a MMRM, with treatment group and analysis visit as factors and Baseline score for related assessment and weight as continuous covariates. Treatment group by analysis visit and Baseline related assessment by analysis visit will be included as interaction terms in the model. An unstructured covariance matrix will be assumed. If covariance matrix will not converge then other covariance structure will be used like compound symmetry, autoregressive structure etc. The treatment effect for the secukinumab T2T regimen at different analysis visits will be determined from the pairwise comparison performed between the 2 treatment groups. The adjusted least square means, point estimate of difference between treatment means, 95% CI for treatment difference and p-value will be presented.

2.7.3 Handling of missing values/censoring/discontinuations

Non-responder imputation will be applied to all secondary response variables. In case of substantial missing data in the secondary analysis, alternative approaches will be assessed by repeating the logistic regression model using ways to handle missing values. These may include, but are not limited to:

- Multiple imputation
- Observed data analysis

2.8 Safety analyses

Safety measurements include duration of exposure, vital signs, laboratory data and adverse events. All safety endpoints will be summarized using the Safety Set. Patients will be analyzed according to treatment received. No imputation will be carried out for missing data.

2.8.1 Adverse events (AEs)

All information obtained on AEs will be displayed by treatment group and subject. Summary tables for AEs will summarize only on-treatment events, with a start date during the on-treatment period (see [Section 2.1.1](#) for definition of on-treatment period).

The count of treatment-emergent AEs, number (and percentage) of subjects with treatment-emergent AEs (defined as events started after the first dose of study treatment or events present prior to start of study treatment but increased in severity based on PT) will be summarized in the following ways:

- By treatment, primary system organ class and PT.
- By treatment, primary system organ class, PT and maximum severity.

Adverse events in the T2T arm will be summarized by 3 groups (secukinumab 150 mg, secukinumab 300 mg and adalimumab 40 mg).

Adverse events occurring in the SOC arm for patients treated with any of the following: secukinumab 150 mg, secukinumab 300 mg, adalimumab 40 mg and other will also be summarized under a separate SOC page.

Separate summaries will be provided for study treatment related AEs, death, SAEs, other significant AEs action taken leading to study drug withdrawn and AEs leading to dose adjustment (dose increase, dose reduce).

Adverse events will be summarized by presenting, for each treatment group, the number and percentage of patients having any AE, having an AE in each primary system organ class and having each individual AE (PT). Summaries will also be presented for AEs by severity and for study treatment related AEs. If a patient reported more than one AE with the same PT, the AE with the greatest severity will be presented. System organ classes will be presented in alphabetical order, preferred terms will be sorted within system organ class in descending frequency of AEs in the T2T treatment group. If a subjects reported more than one AE within the same primary system organ class, the patient will be counted only once with the greatest severity at the system organ class level, where applicable.

For the legal requirements of ClinicalTrials.gov and EudraCT, 2 required tables on treatment emergent AEs which are not serious adverse events with an incidence greater than 5% and on treatment emergent SAEs and SAEs suspected to be related to study treatment will be provided by system organ class and PT on the safety set population.

If for the same patient, several consecutive AEs (irrespective of study treatment causality, seriousness and severity) occurred with the same system organ class and PT:

- a single occurrence will be counted if there is ≤ 1 day gap between the end date of the preceding AE and the start date of the consecutive AE.
- more than one occurrence will be counted if there is > 1 day gap between the end date of the preceding AE and the start date of the consecutive AE.

For occurrence, the presence of at least one SAE / SAE suspected to be related to study treatment / non SAE has to be checked in a block e.g., among AEs in a ≤ 1 day gap block, if at least one SAE is occurring, then one occurrence is calculated for that SAE.

The number of deaths resulting from SAEs suspected to be related to study treatment and SAEs irrespective of study treatment relationship will be provided by system organ class and PT.

In addition, all the treatment emergent AEs will be listed.

The by-subjects listing will include, SOC/PT/Verbatim term, start date, end date, severity, relationship to study drug, whether or not it is a serious AE, action taken with study drug and outcome. Duration will be calculated as (end date – start date + 1) and for ongoing AE (last visit date – start date + 1).

A summary of action taken with number and percentage of subjects will be presented with dose increased, no dose change, dose reduced, drug interrupted, drug withdrawn, not applicable and unknown.

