4. Whether it constitutes a SAE (see [Section 10.1.3](#) for definition of SAE) and which seriousness criteria have been met.
5. Action taken regarding investigational treatment and other treatment.

All AEs must be treated appropriately. Treatment may include one or more of the following:

- Dose not changed

- Dose reduced/increased
- Drug interrupted/withdrawn.

6. Its outcome (not recovered/not resolved; recovered/resolved; recovering/resolving, recovered/resolved with sequelae; fatal; or unknown).

Conditions that were already present at the time of informed consent should be recorded in the patient's medical history.

Adverse events (including laboratory abnormalities that constitute AEs) should be described using a diagnosis whenever possible, rather than individual underlying signs and symptoms.

Adverse event monitoring should be continued for at least 20 weeks (or 5 half-lives or end of study visit, whichever is longer) following the last dose of study treatment.

Once an AE is detected, it must be followed until its resolution or until it is judged to be permanent (e.g. continuing at the end of the study), and assessment should be made at each visit (or more frequently, if necessary) of any changes in severity, the suspected relationship to the investigational drug, the interventions required to treat it, and the outcome.

Information about common side effects already known about the investigational drug can be found in the IB. This information will be included in the patient informed consent and should be discussed with the patient during the study as needed. Any new information regarding the safety profile of the medicinal product that is identified between IB updates will be communicated as appropriate, for example, via an IN or an aggregate safety finding. New information might require an update to the informed consent and has then to be discussed with the patient.

Abnormal laboratory values or test results constitute AEs only if they fulfill at least one of the following criteria:

- they induce clinical signs or symptoms
- they are considered clinically significant
- they require therapy

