12.5.2 Analysis of secondary safety endpoints

For all safety analyses, the Safety Set will be used. All listings and tables will be presented by treatment group.

Safety summaries (tables, figures) will include only data from the on-treatment period with the exception of Baseline data, which will also be summarized where appropriate (e.g. change from Baseline summaries). In addition, a separate summary for death including on-treatment and post-treatment deaths will be provided. In particular, summary tables for AEs will summarize only on-treatment events, with a start date during the on-treatment period (i.e. treatment-emergent AEs as defined below).

The on-treatment period lasts from the date of first administration of study treatment to 30 days after the date of the last actual administration of any study treatment.

Adverse events

All information obtained on AEs will be displayed by treatment group and patient.

The number (and percentage) of patients with treatment-emergent AEs (defined as events started after the first dose of study medication or events present prior to start of study treatment but increased in severity based on PT) will be summarized in the following ways:

- By treatment, primary system organ class and PT.
- By treatment, primary system organ class, PT and maximum severity.
- By treatment, standardized MedDRA query and PT.

Separate summaries will be provided for study medication related AEs, death, SAEs, other significant AEs leading to discontinuation, AEs leading to dose adjustment and AE of special interest.

Adverse events will be summarized by presenting, for each treatment group, the number and percentage of patients having any AE, having an AE in each primary system organ class and having each individual AE (PT). Summaries will also be presented for AEs by severity and for study treatment related AEs. If a patient reported more than one AE with the same PT, the AE with the greatest severity will be presented. If a patient reported more than one AE within the same primary system organ class, the patient will be counted only once with the greatest severity at the system organ class level, where applicable. Serious adverse events will also be summarized.

Vital signs

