
• To demonstrate that the efficacy of the T2T approach (with secukinumab as first-line biologic) is superior to the SOC approach based on the percentage of subjects achieving ASAS 20% response (ASAS20), ASAS partial remission (PR), and Bath Ankylosing Spondylitis Disease Activity Index 50% response (BASDAI50) responses at Week 12 and Week 24.• To demonstrate that the T2T approach (with secukinumab as first-line biologic) is superior to the SOC approach in terms of improvement of disease activity, function, axial mobility, and quality of life measures at Week 12 and Week 24 as compared to Baseline according to:
◦ BASDAI◦ ASDAS◦ C-Reactive Protein (CRP) and Erythrocyte Sedimentation Rate (ESR)◦ Bath Ankylosing Spondylitis Functional Index (BASFI)◦ Bath ankylosing spondylitis metrology index (BASMI) and chest expansion◦ Global assessment of disease activity (patient/physician) and general pain on Visual Analog Scale (VAS)◦ ASAS health index (ASAS-HI)◦ Short Form Health Survey (SF-36)◦ Ankylosing Spondylitis Quality of Life (ASQoL)◦ Functional Assessment of Chronic Illness Therapy - Fatigue (FACIT-Fatigue).• To demonstrate overall safety and tolerability of secukinumab.	
• Percentage of subjects achieving ASAS20, ASAS PR, BASDAI50 responses at Week 12 and Week 24.• Improvement of disease activity, function, axial mobility, and quality of life measures at Week 12 and Week 24 as compared to Baseline according to:
◦ BASDAI◦ ASDAS◦ CRP and ESR◦ BASFI◦ BASMI and chest expansion◦ Global assessment of disease activity (patient/physician) and general pain on the VAS◦ ASAS-HI◦ SF-36◦ ASQoL◦ FACIT-Fatigue• The number (and percentage) of patients with treatment-emergent adverse events (AEs).

2 Statistical methods

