Baseline and post-Baseline: Baseline value refers to the value of the last non-missing measurement collected prior to administration of the first dose of study treatment (screening or Baseline visit). A post-Baseline value refers to a measurement taken after the first dose of study treatment.

Change from Baseline: The difference of measure between post-Baseline and Baseline is called change from Baseline.

Percent change from Baseline: The percent change from Baseline will be calculated as below:
 $((\text{post-Baseline value} - \text{Baseline value}) / \text{Baseline value}) * 100$.

On-treatment period: The on-treatment period lasts from the date of first administration of study treatment to 30 days after the date of the last actual administration of any study treatment or end of treatment phase, whichever is later.

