5.1.2 AE date imputation

The following table explains the notation used in the logic matrix. Please note that **missing start dates** will not be imputed.

	Day	Month	Year
Partial Adverse Event Start Date	Not used	MON	YYYY
Treatment Start Date (TRTSTD)	Not used	TRTM	TRTY

	NON MISSING	MON < TRTM	MON = TRTM	MON > TRTM
YYYY MISSING	NC Uncertain	NC Uncertain	NC Uncertain	NC Uncertain
YYYY < TRTY	(D) Before Treatment Start	(C) Before Treatment Start	(C) Before Treatment Start	(C) Before Treatment Start
YYYY = TRTY	(B) Uncertain	(C) Before Treatment Start	(A) Uncertain	(A) After Treatment Start
YYYY > TRTY	(E) After Treatment Start	(A) After Treatment Start	(A) After Treatment Start	(A) After Treatment Start

The following table is the legend to the logic matrix.

If AE end date is complete and AE end date < Treatment start date or AE end date is partial and AE imputed end date < Treatment start date, then AE start reference = min (informed consent date, earliest visit date from SV) Else if AE end date is partial,AE end date > = Treatment start date or AE is ongoing , then AE start reference = treatment start date.

Relationship	Time imputation
Before AE start reference	Partial date indicates AE start date prior to AE start reference
After AE start reference	Partial date indicates AE start date after AE start reference
Uncertain	Partial date insufficient to determine relationship of AE start date to AE start reference
Imputation Calculation	
NC/Blank	No convention
(A)	MAX(01MONYYYY, AE start reference+1 day)

Relationship	Time imputation
(B)	AE start reference+1
(C)	15MONYYYY
(D)	01JULYYYY
(E)	01JANYYYY
Complete date	No date imputation

If time is captured for the study
Case1: if AE start date is not equal to AE start reference then do the following:
 If minutes missing then AESTMF = M and time is imputed to hh:00
 If minutes missing then AESTMF = H and time is imputed to 00:00
Case2: if AE start date = AE start reference then AESTMF = H and time is imputed to treatment start time + 1 hour

Adverse Event End Date Imputation

Imputed date = date part of original date, if complete date.

Imputed date = min (completion/discontinuation visit date, DEC 31, date of death), if month is missing.

Imputed date = min (completion/discontinuation visit date, last day of the month, date of death), if day is missing.

Adverse Event End Time Imputation

If the AE end date is complete and time is captured in the study then:

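### The AE tables are limited to events that start on treatment, while the same section also counts pre-dose events that worsen as treatment-emergent; the conflict is unresolved and the tables may be undercounted

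*SAP*

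**What the plan says.** SAP 2.8.1 gives two rules for the AE tables in consecutive paragraphs.

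- **Filter:** "Summary tables for AEs will summarize only on-treatment events, with a start date during the on-treatment period".
- **Definition:** the summaries count treatment-emergent AEs, meaning events that start after the first dose and also "events present prior to start of study treatment but increased in severity based on PT".

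SAP 2.1.1 fixes the lower bound of the window: "The on-treatment period lasts from the date of first administration of study treatment to 30 days after the date of the last actual administration", or to the end of the treatment phase if that is later.

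Protocol 12.5.2 has the same pair and treats them as one set. Its tables keep events "with a start date during the on-treatment period (i.e. treatment-emergent AEs as defined below", and the definition that follows includes pre-existing events that worsen. SAP section 4 declares no change from the protocol analyses.

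On recording, Protocol 10.1.1 requires a detected AE to be followed, and says "assessment should be made at each visit (or more frequently, if necessary) of any changes in severity". On dates, SAP 5.1.2 says that missing AE start dates "will not be imputed", and its matrix has no convention when the year is missing.

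The number and percentage of patients with treatment-emergent AEs is the only safety endpoint listed in SAP 1.2 and in the visible part of Protocol Table 2-1.

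**The concern.** An event that began before the first dose cannot have a start date on or after it. So the filter, read literally, excludes the kind of record that the second half of the definition appears meant to include. A pre-dose AE that becomes worse on study drug is a standard reason for having a two-part definition, and losing it is an error in the unsafe direction.

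Such records can plausibly exist. AEs are collected from consent (Protocol 10.1.1), and screening can last up to 8 weeks (Protocol 8.1), so there is a real interval in which an AE can start before treatment.

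At stake are the headline patient count, the tables by preferred term and by maximum severity, and, if the filter is applied to every summary, the treatment-emergent tables prepared for the public registries. With two rules and no statement of which one governs, the choice falls to whoever programs the tables.

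**Working it through.** The plan states no AE rate, so there is no figure to reproduce. The check has two parts.

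**1. Apply both rules to each type of record**

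| Record | Start-date filter | Treatment-emergent definition |
|---|---|---|
| New event on treatment | in | in |
| Pre-dose event, not worsened | out | out |
| Pre-dose AE, worsened, original start date kept | **out** | **in** |
| Worsening entered as a new record of the same preferred term, dated on treatment | in | in |

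The rules disagree for one dated record type only. Whether that type arises depends on data entry, and the text points both ways:

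- *Towards one continuing record:* severity is reassessed at each visit (Protocol 10.1.1), and progression of an SAE is reported as follow-up to the first report (Protocol 10.1.3).
- *Towards a new record:* conditions present at consent go to medical history (Protocol 10.1.1); the AE wording inside the SAE definition covers worsening of something pre-existing (Protocol 10.1.2); and SAP 2.8.1 provides for consecutive events of the same preferred term regardless of severity.

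Neither document says which is done.

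An AE with no start date is a separate gap. It fails the filter, but it cannot be shown to meet the definition either, so this is a missing default and not a conflict between the two rules.

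**2. Illustrate the size on the patient-level endpoint**

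A patient drops out of the headline count only if the excluded event is that patient's sole treatment-emergent AE. Let

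- w = share of patients with a pre-dose AE that worsens under its original start date (assumed 1% to 5%),
- u = share of those patients with no other treatment-emergent AE (assumed 20% to 50%),
- n = 150 per arm (planned size, Protocol 12.7.1 and SAP section 3).

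Loss in percentage points = 100 × w × u. Loss in patients = n × w × u.

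- Low: 100 × 0.01 × 0.20 = 0.2 points; 150 × 0.01 × 0.20 = 0.3 patients.
- Middle: 100 × 0.03 × 0.35 = 1.05 points; 150 × 0.03 × 0.35 = 1.6 patients.
- High: 100 × 0.05 × 0.50 = 2.5 points; 150 × 0.05 × 0.50 = 3.75 patients.

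Both w and u are assumptions; the documents supply neither. Event counts and the tables by preferred term or maximum severity are not shielded by u in this way, because there the worsened event is missing even when the patient has other AEs.

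**The case against.** The best defence is that the documents regard the two rules as the same set. Protocol 12.5.2 links them explicitly, nothing says that the filter overrides the definition, and SAP 2.8.1 says that treatment-emergent AEs, so defined, are what is summarized. If sites enter each worsening as a new AE with its own date, both rules give the same tables. The second half of the definition then simply confirms that such an event counts even though the condition was already there. In addition, all treatment-emergent AEs are listed, start dates are required AE items (Protocol 10.1.1), missing values are queried (Protocol 11.2), and no hypothesis test depends on these tables.

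Much of this stands, and it rules out two stronger readings.

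- *A reader might infer that the safety endpoint is undercounted as a matter of fact.* The documents do not support that. It requires both that worsenings stay under their original dates and that the filter is applied over the definition, and neither is stated.
- *A reader might take the number of patients with an affected event as the number lost.* For example, if 5% to 15% of 300 patients had an AE ongoing at first dose and 10% to 30% of those worsened, 300 × 0.05 × 0.10 = 1.5 to 300 × 0.15 × 0.30 = 13.5 patients would have such an event. Those rates are also assumed, and most of those patients could still be counted through another AE.

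What the defence does not do is settle the matter. Linking two rules that differ does not make them agree. No text requires a new record for a worsening. A listing does not correct a table's counts or percentages. Querying reduces missing dates but gives no rule for those that remain.

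**Conclusion.** The conflict is on the page, and neither document resolves it. Applied literally, the filter drops an AE that began between consent and first dose and worsened under its original start date, and an AE with a fully missing start date. The treatment-emergent AE tables may therefore be undercounted.

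The true size cannot be calculated from the documents. The effect on the patient-level percentage is probably small: the illustration in the working stays at or below 2.5 percentage points, and it would be zero if every worsening is entered as a new dated record and no start date is missing. The preferred-term and maximum-severity tables are the more exposed. The point is worth correcting because it leaves an unstated programming choice inside the only stated safety endpoint.

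**What to change.** In SAP 2.8.1, with Protocol 12.5.2 aligned to it:

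1. Make the treatment-emergent definition govern the AE summary tables: include AEs whose onset **or** worsening falls in the on-treatment period.
2. State how a worsening is recognized. Either a worsening of a pre-dose AE is entered as a new record with its own start date, or it is identified by comparing on-treatment severity with the maximum pre-dose severity for the same preferred term.
3. Count an AE with a fully missing start date as treatment-emergent unless its end date is before the first dose. This matches how SAP 5.1.2 already leans: when a partial start date leaves the order uncertain and the AE is ongoing or ended on or after the first dose, the start is placed after treatment start.

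**Cost.** AE counts rise slightly. The change is more than a line of code, because the worsening must be dated or recorded separately. The AE items in Protocol 10.1.1 and the listing in SAP 2.8.1 show a severity grade, a start date and an end date, but no date of severity increase. If the eCRF holds only one grade per event, a worsening under its original date could not be recovered afterwards, and the SAP should then state that limit.
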